4.4.4 Follow-up assessment

Follow-up assessment will take place within 5 days of the final day of the 28-day intervention. The follow-up assessment is planned to take place at the RICE Centre. However, due to the uncertainty of the ongoing COVID-19 pandemic, there is the possibility of future lockdowns being implemented, or the participant being required to self-isolate whilst enrolled in the study. As the exercise snacking intervention is deliberately intended to be performed in the home the intervention should be able to continue uninterrupted, provided that the participant will not be alone when performing the exercise bouts. In the event that participants are not able to attend the testing facility for follow up assessment, this may be conducted remotely using video calling. This approach was successfully implemented in a recent study conducted whilst older adults were following government guidance to 'shield' during March to June 2020 [26]. However, in the aforementioned study, older adults without physical access to the information and communications technology (ICT) capable of video calling or lacking the digital literacy to use video calling software, were not able to take part in the study. To address this in the present study, tablets with pre-paid sim card/wifi dongles will be provided, along with written instructions for use of a GDPR compliant video calling software. The questionnaire-based assessments will still be completed on paper forms during the follow-up assessment video call, and they will be delivered with the tablet.

Questionnaires will be completed in the same order as the baseline assessment, but preceded by an additional questionnaire based on the theoretical framework of acceptability (TFA), which contains 8 items measuring general acceptability and the 7 distinct components of the framework [27] to assess acceptability of the exercise snacking intervention. Participants will repeat the same tests of physical function as completed in the baseline assessment (including the SPPB previously completed in the screening), under the same conditions as previously.

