To complete the physical function tests remotely participants must be accompanied at all times by someone else (e.g. carer or another member of the household). Researchers will instruct the participant on where to place the tablet and chair for the SPPB chair test and STS-60 for a view that allows the test to be carried out as in the baseline assessment. For the balance measures of the SPPB and static standing balance measures, the participant will be reminded that they can position a stable item nearby in case they feel at risk of losing balance. The 2.4 m walk element of the SPPB and the TUG will be omitted in cases where the follow-up testing is completed remotely.

Qualitative assessment of experience of the protocols: Following the intervention participants will be invited to take part in an interview to provide qualitative feedback on their experience of the intervention. Interviews will take place in person or via video calling accordingly, will be digitally recorded, transcribed verbatim and anonymized on completion. The interview schedule will cover; (i) participants' perceptions of the impact of exercise snacking on mood, appetite, vitality, sleep, and other participant-generated concerns, (ii) adherence to the study protocol, i.e., if and how participants adapted the prescribed regimes, and factors they suggest would make the protocol easier to adopt, and (iii) the perceived barriers and facilitators, and costs and benefits of exercise-snacking. Transcripts will be analysed systematically using framework analysis to highlight key themes within and across participants, and the results used to facilitate participant input into the feasibility analysis and protocol amendments.

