4.5 Data Analyses

Primary aim: Acceptability of a 28-day exercise snacking intervention in outpatients attending the RICE memory clinic in Bath.

Secondary aims: Changes from pre- to post- exercise-snacking intervention in 1) attitudes to exercise (Outcome Expectancy for Exercise Questionnaire) 2) self-confidence for exercise (Barrier Self-efficacy Scale), 3) psychological need satisfaction- for exercise (PNSE)) 4) current mental health (Patient Health Questionnaire, Generalised Anxiety Disorder Assessment and Subjective Vitality Index), 5) general health (Short Form Health Survey) 6) quality of life (Life Satisfaction Scale, Global Quality of Life Scale 7) cognitive assessment (MOCA and GFI), and 8) physical function assessments of (SPPB, STS-60, RPE for STS-60,standing balance scores, and TUG).

Statistical analyses: The primary outcome of acceptability of the exercise snacking intervention will be assessed qualitatively using reflexive thematic analysis, and descriptively based on the scores from the TFA questionnaire. Together this information will highlight aspects of the programme that may pose a challenge to implementation or warrants further consideration as to how to optimise engagement and utility for the users. Student's T-test will be used to identify changes in secondary aims, i.e. change in questionnaire scores and functional outcomes from pre-to-post-intervention. Statistical significance will be accepted at $P < 0.05$. Effect sizes will also be calculated according to Cohen [28], with $d > 0.08$ considered a large effect.

5. Inclusion / Exclusion Criteria

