A single password protected Excel data sheet maintained on a RICE computer will be used to record participant names and relevant contact information associated with a given participant ID code. This will exist for logistical purposes of running the study, and only the designated researchers will have access to this identifying information. All other non-identifying participant information and results will be stored on Excel data sheets with the participant ID code only.

For participants that opt it, an audio recording of a qualitative interview undertaken at the second visit to RICE will be taken. The information provided will be transcribed and analysed later with all identifying information removed. The audio file will be deleted once the information has been transcribed.

Any results published from this study will be anonymous and include no identifiable information.

10. References

1. Mitchell, W.K., et al., *Sarcopenia, dynapenia and the impact of advancing age on human skeletal muscle size and strength; a quantitative review*. *Frontiers in Physiology*, 2012. **3**.
2. Degens, H. and M.T. Korhonen, *Factors contributing to the variability in muscle ageing*. *Maturitas*, 2012. **73**(3): p. 197-201.
3. Seene, T. and P. Kaasik, *Muscle weakness in the elderly: role of sarcopenia, dynapenia, and possibilities for rehabilitation*. *European Review of Aging and Physical Activity*, 2012. **9**(2): p. 109-117.
4. Sousa, A.S., et al., *Financial impact of sarcopenia on hospitalization costs*. *Eur J Clin Nutr*, 2016. **70**(9): p. 1046-51.
5. Pinedo-Villanueva, R., et al., *Health Care Costs Associated With Muscle Weakness: A UK Population-Based Estimate*. *Calcified Tissue International*, 2019. **104**(2): p. 137-144.
6. Scuffham, P., S. Chaplin, and R. Legood, *Incidence and costs of unintentional falls in older people in the United Kingdom*. *Journal of Epidemiology and Community Health*, 2003. **57**(9): p. 740-744.
7. Comans, T.A., et al., *The increase in healthcare costs associated with frailty in older people discharged to a post-acute transition care program*. *Age Ageing*, 2016. **45**(2): p. 317-20.
8. Faulkner, J.A., et al., *Age-related changes in the structure and function of skeletal muscles*. *Clinical and Experimental Pharmacology and Physiology*, 2007. **34**(11): p. 1091-1096.

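### Does naming two qualitative methods, with no step matching each interview to that participant's TFA scores, undermine the acceptability analysis?

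*Combined protocol and SAP*

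**What the plan says.** Section 4.4.4 (Follow-up assessment) describes one set of interviews after the intervention, by invitation. The topics include "the perceived barriers and facilitators, and costs and benefits of exercise-snacking". On analysis it says "Transcripts will be analysed systematically using framework analysis to highlight key themes within and across participants", with "the results used to facilitate participant input into the feasibility analysis and protocol amendments". The recordings "will be digitally recorded, transcribed verbatim and anonymized on completion".

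The same section describes the TFA questionnaire, given at the same follow-up, "which contains 8 items measuring general acceptability and the 7 distinct components of the framework".

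The Data Analyses section assigns methods to the primary outcome. It says "The primary outcome of acceptability of the exercise snacking intervention will be assessed qualitatively using reflexive thematic analysis", and that the TFA scores are summarised descriptively. It then gives the purpose of using both: "Together this information will highlight aspects of the programme that may pose a challenge to implementation".

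Section 9 (Confidentiality) keeps non-identifying information and results under a participant ID code. On the recordings it says: "The audio file will be deleted once the information has been transcribed".

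**The concern.** Two methods are named for what looks like a single set of transcripts. Framework analysis is attached to feasibility and amendments, and reflexive thematic analysis to acceptability. The purposes overlap, because the interview topics on barriers and costs are what an acceptability analysis would draw on. Two analysts, each following one section, could arrive at different theme sets, and the plan has no rule on which is primary.

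The second worry is the joint reading. Only framework analysis comes with an explicit look inside each participant's account, and it is not assigned to acceptability by name. The plan could therefore deliver a set of themes and a TFA summary without showing whether the barriers came from people who rated the programme well or badly. If transcripts lost their study code when anonymised, that comparison could not be recovered later. Acceptability is the primary outcome of a pilot without a formal sample size calculation, so the qualitative work carries much of the conclusion.

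**Working it through.** The plan gives no figure on this point, so there is nothing to reproduce. The check is mainly a comparison of the sections.

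**1. Do the method names conflict?** Yes. Section 4.4.4 says framework analysis and the Data Analyses section says reflexive thematic analysis. No other qualitative data have a planned analysis, and neither section refers to the other. A division by purpose (acceptability for one, feasibility and amendments for the other) fits the text but is not stated.

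**2. Is reflexive thematic analysis the tool for combining interviews and scores?** No. The Data Analyses section applies it to the qualitative part only. TFA scores are handled descriptively, and the two outputs are then considered together.

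**3. At what level are they combined?** The stated target is aspects of the programme. Themes about what was hard, beside summaries of 8 TFA items (1 general + 7 components), address that target directly. No section promises a person-by-person comparison, so its absence breaks no commitment. Assigning framework analysis to acceptability would not bring in the TFA scores either.

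**4. Are the interviews cut off from acceptability?** No. Section 2 justifies the qualitative approach in the paragraph that stresses the need to assess acceptability. Section 4.4.1 places the acceptability questionnaire and the interview in the same follow-up assessment.

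**5. Would the link be lost?** The documents do not say so. Removing identifying details from a transcript does not require removing a study code, and section 9 holds results under that code. An analysis inside each participant's account needs transcripts that stay distinguishable. Deleting audio after transcription does not break a code on the transcript. The plan does not state that transcripts carry the code, which is a missing detail.

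**6. How much could separate totals hide?** Inputs: n = 20 completers (section 4.3), all assumed interviewed; a = number with a favourable general rating (assumed); b = number describing a substantial barrier (assumed). The overlap lies between max(0, a + b − n) and min(a, b).

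| a | b | Lower bound | Upper bound | Share of favourable raters |
|---|---|---|---|---|
| 16 | 4 | max(0, 0) = 0 | 4 | 0/16 to 4/16 = 0–25% |
| 16 | 8 | 16 + 8 − 20 = 4 | 8 | 4/16 to 8/16 = 25–50% |
| 16 | 12 | 16 + 12 − 20 = 8 | 12 | 8/16 to 12/16 = 50–75% |
| 18 | 8 | 18 + 8 − 20 = 6 | 8 | 6/18 to 8/18 = 33–44% |
| 14 | 8 | 14 + 8 − 20 = 2 | 8 | 2/14 to 8/14 = 14–57% |

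The arithmetic is correct but describes a tally the trial does not plan. The documents define neither a favourable cut-off nor a substantial barrier. Interviews are by invitation, so fewer than 20 may exist. Nor does overlap mean that scores overstate acceptability: the schedule raises barriers with every interviewee, and a person can name one and still find the programme acceptable.

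**The case for a change.** The strongest case for a change is that the conflict concerns the primary outcome and would take a sentence or two to settle. A further sentence could plan a display with one row per participant, the 7 TFA components as columns and that person's scores alongside. At 20 participants that is at most 20 × 7 = 140 entries, needs no new data, and would replace the ranges above with exact counts.

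The first part stands as a matter of wording: the two names should agree, or each should be tied to its purpose. It does not amount to a fault in the analysis, because either method applied to these interviews yields themes bearing on acceptability, and analysts would report which they used and for what.

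The second part is a design preference. Section 4.4.4 does not mention a chart or TFA columns, so the display would be new work. Sorting interview material into predefined components also sits awkwardly beside a reflexive thematic analysis, and qualitative analysts would differ on whether to do it. It would need a rule for participants who have scores but no interview. It could be a useful optional addition, but it corrects nothing.

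**Conclusion.** No change to the plan follows. What remains is a minor reporting inconsistency: two method names for what appear to be the same transcripts, with their relation left unstated. The natural reading is that reflexive thematic analysis serves acceptability, since the Data Analyses section is the only place that assigns a method to the primary outcome, and that framework analysis serves feasibility and amendments. Followed that way, the plan gives themes and a TFA summary that are each sound and can be read together for their stated purpose.

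This is a single-cohort exploratory pilot, and no hypothesis test, error rate, sample size or decision threshold is affected. The conclusion assumes that the programme-level purpose in the Data Analyses section is the intended one, and that ordinary practice keeps the study code on anonymised transcripts. A commitment elsewhere to participant-level comparison would make the missing step a real omission, but the documents contain none.

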4.5 Exercise snacking intervention

The exercise snacking requires only a stable kitchen chair to perform. During all exercise snacking bouts, there must be a carer or a member of the household with functional capacity to request immediate assistance if required. Participants will be asked to perform five exercises, each for one minute followed by one minute of rest. In that minute of exercise, the participant will perform as many controlled repetitions of the given exercise as they can. Participants will be asked to perform the exercise snacks twice daily, ideally once in the morning and once in the afternoon close to mealtimes and separated by at least two hours where possible. The exercises are: sit-to-stand from a chair, seated arm raises to overhead, marching on the spot (holding a chair if necessary), seated arm crossing, and seated calf raises. Participants will be asked to always perform the sit-to-stand exercise first and record the number of repetitions completed in the minute, and thereafter may alternate the order of exercises, but will be asked to record the order in a logbook provided. During the demonstration, participants will be reminded that the aim is to complete as many repetitions as possible during each bout, and that use of the logbook serves to provide the participant with objective feedback on their progress.

4.5 Data Analyses

Primary aim: Acceptability of a 28-day exercise snacking intervention in outpatients attending the RICE memory clinic in Bath.

Secondary aims: Changes from pre- to post- exercise-snacking intervention in 1) attitudes to exercise (Outcome Expectancy for Exercise Questionnaire) 2) self-confidence for exercise (Barrier Self-efficacy Scale), 3) psychological need satisfaction- for exercise (PNSE)) 4) current mental health (Patient Health Questionnaire, Generalised Anxiety Disorder Assessment and Subjective Vitality Index), 5) general health (Short Form Health Survey) 6) quality of life (Life Satisfaction Scale, Global Quality of Life Scale 7) cognitive assessment (MOCA and GFI), and 8) physical function assessments of (SPPB, STS-60, RPE for STS-60,standing balance scores, and TUG).

Statistical analyses: The primary outcome of acceptability of the exercise snacking intervention will be assessed qualitatively using reflexive thematic analysis, and descriptively based on the scores from the TFA questionnaire. Together this information will highlight aspects of the programme that may pose a challenge to implementation or warrants further consideration as to how to optimise engagement and utility for the users. Student's T-test will be used to identify changes in secondary aims, i.e. change in questionnaire scores and functional outcomes from pre-to-post-intervention. Statistical significance will be accepted at $P < 0.05$. Effect sizes will also be calculated according to Cohen [28], with $d > 0.08$ considered a large effect.

5. Inclusion / Exclusion Criteria

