4.1 Research Design

This is a single cohort acceptability study. All participants will receive the intervention, and pre- and post-testing.

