4.3 Sample Size

The novel exercise snacking intervention to improve muscle function has not been studied in a clinical population of older adults before, and as such the acceptability of exercise snacking in this population is unknown. Furthermore, there is a lack of comparable literature to inform a quantitative sample size calculation to assess changes in muscle function as a primary outcome measure in this population, particularly given adherence rates are yet to be established. Therefore, in order to assess the acceptability of the intervention, it is estimated that 20 participants will be required to complete all follow-up assessments. A capped rolling recruitment strategy will be employed whereby if up to 10 participants drop-out of the intervention and do not complete follow-up assessments, they will be replaced. Participants who drop out of the intervention but agree to complete the follow-up assessments will not be replaced. For the sake of pragmatism, no more than 10 additional participants will be recruited.

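### The printed cut-off for a large effect, d > 0.08, is implausibly small, and chance alone would often exceed it

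*Combined protocol and SAP*

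**What the plan says.** The statistical analyses paragraph of section 4.5 (Data Analyses) gives one rule for judging effect size: "Effect sizes will also be calculated according to Cohen [28], with $d > 0.08$ considered a large effect". It defines no small or medium band, and no other cut-off appears in the document. It does not say which SD standardises d.

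The rule sits beside the significance test for the secondary outcomes (a Student's "T-test will be used to identify changes in secondary aims, i.e. change in questionnaire scores and functional outcomes"), with significance at P < 0.05. The design in section 4.1 is a single cohort: "All participants will receive the intervention, and pre- and post-testing". For the number of participants, section 4.3 says "it is estimated that 20 participants will be required to complete all follow-up assessments". That number does not come from a power calculation, because "there is a lack of comparable literature to inform a quantitative sample size calculation".

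The primary outcome does not use the rule: "The primary outcome of acceptability of the exercise snacking intervention will be assessed qualitatively using reflexive thematic analysis", with a descriptive summary of the acceptability questionnaire scores.

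**The concern.** A threshold of 0.08 calls a result large when the mean has moved by less than a tenth of a standard deviation. That is a very small change on any outcome, and it sits oddly with a rule that presents itself as a published convention.

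This is a current, pre-specified rule of interpretation, not background text. The study has no control group and its secondary outcomes are not powered, so effect sizes will carry much of the quantitative message. Followed literally, the rule would let trivial or purely random pre-post differences in physical function, mood or quality of life be reported as large effects.

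**Working it through.** The plan contains no calculation behind 0.08, so there is no figure to reproduce. The check is how often the rule as printed would be met if nothing had changed.

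**Inputs from the document**
- Cut-off: d > 0.08 (section 4.5, Data Analyses).
- Completers: n = 20 (section 4.3). Replacement of drop-outs is capped ("no more than 10 additional participants will be recruited"), but the target stays at 20.
- Measures: 16 in the list of secondary aims. There are 11 questionnaires and cognitive or frailty instruments (exercise attitudes 1, self-confidence 1, need satisfaction 1, mental health 3, general health 1, quality of life 2, MOCA and GFI 2) and 5 physical function measures. This assumes one score per measure and counts standing balance once; counting its four stances separately gives 19.

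**Assumptions, because the plan is silent**
- The t-test is paired.
- d = mean change / SD of change, with other standardisers tried below.
- True change is zero and scores are normally distributed.

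**Main calculation.** With this d, t = d × √n on n − 1 degrees of freedom.
- At 0.08: t = 0.08 × √20 = 0.358 on 19 df. P(d > 0.08) = 0.362 and P(|d| > 0.08) = 0.724.
- At 0.8: t = 0.8 × √20 = 3.578. P(|d| > 0.8) = 0.0020.
- Other cut-offs, in case reference 28 gives another value: 0.5 gives 0.038 and 1.0 gives 0.0003 (either direction).

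As printed, the rule covers positive d only. Some outcomes improve by falling, such as the TUG time, so the count in practice depends on a sign convention that the plan does not give. Both readings are therefore shown.

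**Expected number of labels due to chance.** Expected counts add up whether or not the outcomes are correlated.
- 16 measures at 0.08: 16 × 0.362 = 5.8 (one direction); 16 × 0.724 = 11.6 (either).
- 19 measures at 0.08: 19 × 0.362 = 6.9; 19 × 0.724 = 13.8.
- 16 measures at 0.8: 16 × 0.0020 = 0.03 (either).

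**Other standardisers.** If d uses a raw-score SD, the result depends on the pre-post correlation r, which the plan does not give. Simulation with n = 20:

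| Standardiser | r | P(d > 0.08) | P(\|d\| > 0.08) |
|---|---|---|---|
| Baseline SD | 0.3 | 0.382 | 0.766 |
| Average SD | 0.3 | 0.382 | 0.764 |
| Baseline SD | 0.7 | 0.325 | 0.651 |
| Baseline SD | 0.9 | 0.217 | 0.433 |
| Average SD | 0.9 | 0.217 | 0.433 |

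Over this range the expected labels among 16 measures run from 16 × 0.217 = 3.5 to 16 × 0.382 = 6.1 in one direction, and from 16 × 0.433 = 6.9 to 16 × 0.766 = 12.3 in either. At 0.8 the largest either-direction rate over the same range is 0.0071.

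**Fewer pairs.** Section 4.4.4 says "the TUG will be omitted in cases where the follow-up testing is completed remotely", and the same sentence drops the walking element of the SPPB. The TUG and the full SPPB score may therefore have fewer than 20 pairs. At an assumed n = 16, t = 0.08 × √16 = 0.32 on 15 df, giving 0.377 in one direction and 0.753 in either.

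**The case against.** Four points can fairly be made on the other side.

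- **Detectability is not magnitude.** With 20 pairs, d = 0.08 gives P = 0.72, and the smallest d reaching two-sided P < 0.05 is 0.468. Neither fact proves that 0.08 is not large, since a big effect can be non-significant in a small sample. This is right. The case rests on 8% of one SD being a very small change, and on how often chance exceeds it.
- **The intended value is inferred.** The figure 0.8 is printed nowhere, reference 28 is not available here, and an error in reading the PDF cannot be wholly excluded. This also stands, so 0.8 is a value to confirm. That 0.08 is unsuitable does not depend on it.
- **The harm needs literal use.** An analyst who consults the cited reference may apply another value, and each label would appear beside a P value that is often non-significant. This lowers the risk of misleading a reader, but the written rule remains wrong.
- **The ranges depend on the correlations chosen.** At r = 0.95 with a raw-score SD the either-direction rate at 0.08 falls to 27%. At r = 0 the rate at 0.8 rises to about 1.6% to 2.1%, depending on the SD. These extremes widen the range but leave the contrast between the two cut-offs intact.

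**Conclusion.** The concern holds. As printed, the threshold would attach the label *large* to chance differences in roughly one third (one direction) to three quarters (either direction) of secondary outcomes, under the main assumptions of 20 pairs, no true change and d standardised by the SD of change. With a raw-score SD and r between 0.3 and 0.9, the rates are about 22% to 38% and 43% to 77%. All of these are conditional on the rule being applied literally.

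Confidence is high that 0.08 is wrong as a cut-off for a large effect. That 0.8 was meant is a strong inference, still to be confirmed. No decision in the plan depends on the label, so this is a small but necessary text correction and not a threat to the study.

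**What to change.** Before analysis, check the figure against reference 28. If 0.8 is confirmed, replace d > 0.08 with d > 0.8 in the statistical analyses paragraph. The cost is one figure in one sentence; the visible effect is that fewer results will be called large.

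Optionally, add a sentence that names the SD used to standardise d, states that the t-test is paired, and commits to a 95% confidence interval with each effect size. With 20 pairs, the interval would tell readers more than the label.
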